9.4 STATISTICAL ANALYSES

9.4.1 GENERAL APPROACH

We will compare the change using an ANOVA for repeated measures in which we assess for the significance of the interaction of treatment allocation and time interval (time_x_group interaction) using SPSS 25.0 (Chicago, IL). Additional exploratory endpoints will include absolute CRP values at 28 days, and the percentage of patients with CRP <2 mg/L at each time point. The interval change in CRP levels from baseline to 28 days will be expressed as median and interquartile range. All reporting will be in conjunction with the CONSORT statement.¹⁹

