1.3 SCHEDULE OF ACTIVITIES (SOA)

	Screening visit (within 30 days)	Randomization / Treatment day 1	28±3 days	60±7 180± days days	
Inclusion/Exclusion criteria and Informed Consent	x	x			
Clinical Assessment (history and physical exam)	x	X	x		
Safety laboratory tests (CBC with diff, CMP, [urine pregnancy at randomization as applicable])			x	x	
Inflammatory biomarkers (hsCRP, IL-6)	x		X		
Quality of life (QoL) assessment	x		X		
Investigational drug dispensing (education on storage and self- administration)		X for anakinra group			
Assessment for adverse events (in-person or by telephone)			x	x x	

Interleukin-1 blockade in cardiac sarcoidosis Protocol MAGiC ART

Arrhythmia assessment with 24-hour ECG Holter	х	Χ ±14 days
[Cardiac magnetic resonance]	[X]	[X] ±14 days
[Cardiac PET scan]	[X] within 60 days	[X] ±14 days

Procedures indicated in [brackets] denote additional testing done as part of the VCU Imaging Substudy.

*_indicates complete blood cell count with differential and comprehensive metabolic profile at each time point, and pregnancy test at initial visit (if applicable)

Considering the ongoing COVID-19 pandemic emergency, the PI will consider potential deviation to the protocol if needed to promote the safe conduct of the research.

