8 STUDY ASSESSMENTS AND PROCEDURES

8.1 EFFICACY ASSESSMENTS

8.1.1 Biomarkers

Blood samples will be taken from a peripheral vein at time of screening, randomization visit and the 28day visit, and used for analysis of inflammatory markers - high-sensitivity C reactive protein (CRP) and Interleukin-6 (IL-6).

Samples will be processed by the Department of Pathology at VCU or UMich, as standard of care tests are processed.

We will compare interval changes in CRP and IL-6 between the 2 groups using an analysis of variance (ANOVA) for repeated measures and assessing for time_x_group interaction.

Additional exploratory analyses will be conducted on cytokines from sera of patients with bioassays available through LabCorp.

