9 STATISTICAL CONSIDERATIONS

9.1 STATISTICAL HYPOTHESES

• Primary Efficacy Endpoint(s):

Interval change in CRP levels from baseline to 28 days

We hypothesize that anakinra will reduce systemic inflammation as shown by CRP levels. CRP will be measured with a widely available high-sensitivity assay able to detect values in the normal range (<2 mg/l). Hs-CRP will be measured at randomization visit and again at 28±3 days. We will use ANOVA for repeated measures and assess time_x_group interaction to determine differences between changes in the anakinra on top of standard of care group versus standard of care only group.

• Secondary Efficacy Endpoint(s):

Interval change in IL-6 levels from baseline to 28 days

We hypothesize that anakinra will reduce systemic inflammation as shown by IL-6 levels. IL-6 will be measured with a widely available ELISA assay . IL-6 will be measured at randomization visit and again at 28±3 days. We will use ANOVA for repeated measures and assess time_x_group interaction to determine differences between changes in anakinra group versus control group.

Interval change in QoL scores at SAT

We hypothesize that anakinra will improve QoL scores on SAT questionnaires. QoL SAT will be measured at enrollment and again at 28±3 days. We will use ANOVA for repeated measures and assess time_x_group interaction to determine differences between changes in anakinra group versus control group

• Additional Efficacy Endpoints(s) for Imaging Substudy available at VCU

[Interval change in T2 mapping at CMR]

[We hypothesize that anakinra will reduce myocardial edema as measured by T2 mapping at CMR. T2 mapping will be completed within 30 days of randomization and again at 28 ± 14 days. We will use ANOVA for repeated measures and assess time_x_group interaction to determine differences between changes in anakinra versus control.]

[Interval change in cardiac FDG-PET inflammation signal]

[We hypothesize that anakinra will reduce myocardial inflammation as measured by cardiac PET signaling. PET signaling will be completed within 60 days of randomization and again at 28 ± 14 days. We will use ANOVA for repeated measures and assess time_x_group interaction to determine differences between changes in anakinra versus control.]

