9.2 SAMPLE SIZE DETERMINATION

Using an informatics-based tool by TriNetX we ran a retrospective analysis of patients seen in the Cardiac Sarcoidosis Clinic at VCU in the past year: we identified 30 subjects with sarcoidosis who had CRP 3-20 mg/L (we excluded patients with CRP>20 mg/L as they may have had concomitant bacterial infection, and therefore could be excluded upon screening). The mean age was 55 years (range 37-82), 55% were men, and 77% were African American. The CRP was 7.64 ±3.74 mg/L (mean±standard deviation). We predict a reduction of CRP by >60% in the anakinra group and no change in standard of care only group. The Table below shows estimated power for CRP reduction between 50% and 75% in the active treatment group (on top of standard of care changes, which are expected to be close to 0), and we evaluated 3 different standard deviation (SD) values starting with 3.74 mg/l which was obtained from our VCU cohort and exploring 0.9x and 1.1x SD.

Power analysis	CRP reduction (estimated mean 7.64 mg/l)					
N=28	50%	55%	60%	65%	70%	75%
SD 3.37 mg/l	85%	91%	95%	97%	99%	>99%
SD 3.74 mg/l	77%	84%	90%	94%	97%	98%
SD 4.11 mg/l	69%	77%	84%	89%	93%	96%

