9.4.2 ANALYSIS OF THE PRIMARY EFFICACY ENDPOINT(S)

We therefore hypothesize that anakinra will reduce systemic inflammation as shown by CRP. CRP will be measured with a widely available high-sensitivity assay able to detect values in the normal range (<2 mg/l). CRP will be measured at enrollment and again at 28±3 days.

Interval change in CRP levels from baseline to 28 days will represent the primary endpoint.

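### The CRP test uses baseline only by subtraction; ANCOVA would raise power for a 60% reduction from about 88% to 94% if the baseline to day-28 correlation is 0.5

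*Combined protocol and SAP*

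**What the plan says.** Three sections name the same test for CRP. Section 9.4.1: "We will compare the change using an ANOVA for repeated measures". Section 8.1.1: "We will compare interval changes in CRP and IL-6 between the 2 groups using an analysis of variance (ANOVA) for repeated measures". Section 9.1: "We will use ANOVA for repeated measures and assess time_x_group interaction". None of them names a baseline covariate, an ANCOVA or a log transformation. Absolute day-28 CRP appears in 9.4.1 only as an extra exploratory endpoint. Section 6.3 stratifies randomization by center and by race/ethnicity, but neither factor is in the model.

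The baseline sample is described in different ways:

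- Section 9.1: "Hs-CRP will be measured at randomization visit and again at 28±3 days".
- Section 9.4.2: "CRP will be measured at enrollment and again at 28±3 days".
- Section 8.1.1: "Blood samples will be taken from a peripheral vein at time of screening, randomization visit and the 28day visit".
- Schedule of Activities (1.3): the inflammatory biomarker row shows marks at screening and day 28 only.

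The power table in 9.2 rests on a clinic cohort with mean CRP 7.64 and SD 3.74 mg/L. It gives 90% power for a 60% reduction with 28 patients.

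**The concern.** With two time points, the time-by-group interaction is the two-sample t-test on change. Subtracting baseline gives it a fixed coefficient of 1, whatever the data say. When the correlation is below 1 and the variances are equal, that over-corrects: regression to the mean adds noise, and a chance baseline difference is carried into the estimate. With 14 per arm and a between-patient SD of 3.74 mg/L, the chance difference in baseline means has an SD of 3.74 × √(2/14) = 1.41 mg/L. At a correlation of 0.5, half of any such difference passes into the change-score estimate.

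Section 4.2 gives the pilot the tasks of looking for a biological signal and estimating an effect size for a later trial. Precision is therefore much of what it has to deliver, and there are only 28 patients, or about 22 after the 20% data loss allowed for in 7.3 (0.8 × 28 = 22.4).

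The unsettled baseline is a second problem and does not depend on any correlation. If all three samples in 8.1.1 entered the ANOVA, the interaction would have 2 degrees of freedom and would no longer test the baseline to day-28 change alone.

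**Working it through.** **Inputs.** From the documents: mean 7.64 and SD 3.74 mg/L (9.2), 28 patients (6.1.1) allocated 1:1, so 14 per arm, and up to 20% loss (7.3). A 60% reduction is 0.6 × 7.64 = 4.584 mg/L. Assumed: two-sided alpha 0.05 (not stated, but it reproduces the table) and the correlation rho (not stated, so shown as a range).

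**Step 1: reproduce the plan's figure.** SE = 3.74 × √(2/14) = 1.414, and 4.584/1.414 − 1.96 = 1.28, giving 90.0% power by the normal approximation. The rest of the table reproduces the same way, so 3.74 acts as the SD of change. The noncentral t (26 df) gives 87.7%.

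**Step 2: variance ratio.** With SD s at both visits, the change score has variance 2s²(1−rho) and the ANCOVA residual has s²(1−rho²). The ratio is (1+rho)/2 whether 3.74 is the SD of change or the SD at one visit. The planned test needs 28 × 2/(1+rho) = 56/(1+rho) patients to match ANCOVA in 28.

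**Step 3: SD of change held at 3.74, 60% reduction, N = 28.** The ANCOVA SD is 3.74 × √((1+rho)/2). The t-based column (25 df) is averaged over chance baseline imbalance and agrees with simulation.

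| Analysis | SD (mg/L) | Power, normal | Power, t | Planned-test N to match |
|---|---|---|---|---|
| Planned test | 3.74 | 90.0% | 87.7% | 28 |
| ANCOVA, rho 0.3 | 3.02 | 98.0% | 96.6% | 43 |
| ANCOVA, rho 0.5 | 3.24 | 96.3% | 94.1% | 37 |
| ANCOVA, rho 0.7 | 3.45 | 94.0% | 91.1% | 33 |
| ANCOVA, rho 0.9 | 3.65 | 91.4% | 87.9% | 30 |

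Before averaging over imbalance, the t-based figure at rho 0.5 is 94.9%.

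**Step 4: 3.74 read as the SD at one visit.** The change SD is then 3.74 × √(2(1−rho)) and the ANCOVA SD 3.74 × √(1−rho²). Planned versus ANCOVA power (normal approximation) is 63.0 vs 90.0% at rho 0, 78.3 vs 92.5% at 0.3, 98.7 vs 99.5% at 0.7, and equal by 0.85. At rho 0.5 the two readings coincide.

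**Step 5: other cases at rho 0.5 (t-based, after imbalance).**

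- 60% reduction, N = 22: 78.1 vs 86.5%.
- 50% reduction, N = 28: 73.9 vs 83.6%.
- 50% reduction, N = 22: 62.5 vs 72.5%.
- 95% CI half-width at N = 28: t(26) × 3.74 × √(2/14) = 2.91 mg/L, against t(25) × 3.74 × √0.75 × √(2/14) = 2.52 mg/L.

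**Step 6: validity.** Simulated type I error was 4.5–5.3% for the planned test and 4.5–5.4% for the ANCOVAs.

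**Step 7: cost of strata terms.** Two terms unrelated to CRP, with near-balanced strata, move power at rho 0.5 from 94.1 to 93.7% (N = 28) and from 86.5 to 85.7% (N = 22).

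**Step 8: three samples in the ANOVA.** Under compound symmetry at rho 0.5, the 2-df interaction has 91.3% power against 87.7% with two samples. Power is not lost, but the hypothesis tested is different.

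**Step 9: log scale.** Assume log-normal CRP with the plan's mean and SD and a proportional 50% reduction, N = 28. At rho 0.3/0.5/0.7, power is 69/81/93% for the planned test, 96/98/99.5% for raw-scale ANCOVA and 97/99/99.9% for log-scale ANCOVA. If the effect also varies between patients (log-SD 0.3), the figures are 66/77/91, 92/94.5/98 and 96/98/99.7%. Baseline adjustment carries most of the gain.

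**The case against.** The planned test is valid, matches the endpoint as defined in 9.4.2, and has about 88–90% power at the predicted effect. The loss is one of efficiency, on an endpoint that is not the trial's primary objective. That stands, and it limits the weight of the point.

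The size of the gain depends on a correlation that the documents do not give, because the cohort in 9.2 has no paired values. That also stands. The variance ratio is firm, but the power gain is known only as a range. The cohort was limited to CRP 3–20 mg/L, while the trial enrolls from 2 mg/L with no upper limit, so every mg/L figure, including the plan's own table, inherits that mismatch. The ratio does not.

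The 94% is for baseline adjustment alone. In a worst case where strata are not held in balance between arms, planned versus fully adjusted power at N = 28 is 87.4 vs 91.8% at rho 0.5, 87.9 vs 88.6% at 0.7 and 88.0 vs 85.0% at 0.9. At N = 22 it is 78.0 vs 77.2% at 0.7 and 78.1 vs 72.7% at 0.9. Stratified randomization should make this unlikely, but the algorithm is not described.

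On the baseline sample, enrollment and randomization may mean the same visit: the quality-of-life score is placed at randomization in 8.1.2 and at enrollment in 9.1. The screening CRP serves eligibility. The Schedule of Activities table is broken in the text copy, so its marks should be checked against the PDF. Even so, 8.1.1 lists three samples and 9.1 two, and no section says which one is the baseline for analysis.

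**Conclusion.** The concern holds. The planned CRP test is an unadjusted comparison of change scores, and it gives up precision that the trial's own data could supply. With equal variances, the ANCOVA estimate has (1+rho)/2 of the planned variance. For 28 patients, a 60% reduction and 3.74 mg/L as the SD of change, the t-based gain from baseline adjustment is about 9 points at rho 0.3, 6 at 0.5, 3 at 0.7 and none at 0.9. With 22 patients and rho 0.5 it is about 8 points.

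These figures assume normal CRP with equal variance in both arms and at both visits. Rho 0.5 follows from the plan only if 3.74 is both the between-patient SD and the SD of change. The change is worth making but is not essential to validity. Naming one baseline sample is needed whichever model is used.

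**What to change.** 1. In 9.4.1 and 9.4.2, make the primary efficacy test an ANCOVA of day-28 hs-CRP on treatment and baseline hs-CRP, with center and race/ethnicity as covariates. Keep the repeated-measures ANOVA as a sensitivity analysis.
2. In 9.4.2, name one baseline sample and bring 8.1.1, 9.1 and the Schedule of Activities into line with it.
3. Optionally, since 9.2 states the effect as a percentage, fit the same model to log hs-CRP and report the ratio of geometric means with its 95% CI, saying how values below the assay limit are entered. This changes the estimand from a mean mg/L difference to a ratio. Under the assumptions above it adds only about 0.4 to 4.5 points over raw-scale ANCOVA.

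**Cost.** The edits are wording in section 9 (and 8.1.1), plus a Schedule of Activities mark if the named sample is not shown there. The Statement of Compliance requires IRB approval of the amendment. No new variable is needed if the sites already draw the named sample. The model spends 1 degree of freedom on baseline and 2 on strata. If the strata are unrelated to CRP, their terms cost 0–0.7 points of power at N = 28 and up to 1.3 at N = 22 when near-balanced, or up to about 4 and 6 points if badly unbalanced. Baseline adjustment alone loses about 1.5 points at rho 0.9 and N = 22.

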9.4.2 ANALYSIS OF THE PRIMARY EFFICACY ENDPOINT(S)

We therefore hypothesize that anakinra will reduce systemic inflammation as shown by CRP. CRP will be measured with a widely available high-sensitivity assay able to detect values in the normal range (<2 mg/l). CRP will be measured at enrollment and again at 28±3 days.

Interval change in CRP levels from baseline to 28 days will represent the primary endpoint.

9.4.3 ANALYSIS OF THE SECONDARY ENDPOINT(S)

We will measure changes in IL-6, an additional inflammatory biomarker as a secondary endpoint. Changes in QoL scores will also be considered a secondary endpoint.

Additional secondary endpoints to be completed as part of the imaging substudy at VCU includes assessment of myocardial edema with T2 mapping at CMR, and myocardial inflammation with cardiac FDG-PET.

9.4.4 SAFETY ANALYSES

The DSMB will monitor the progress of the present trial. The DSMB will meet regularly to review safety data every 6 months or sooner in case of a serious unexpected adverse event that is considered to be possibly, probably or definitely related to the research. All meetings, and specifically any action taken by the committee and the reasons for the actions, will be recorded. These documents will include any data summaries or analyses provided to the DSMB and will remain confidential until the study is concluded. No interim efficacy analyses are planned.

Interim safety analyses will, however, be performed at each meeting. The DSMB will be provided with data related to adverse events. The DSMB may choose to stop enrollment on the basis of safety data observed. If safety concerns are found, further enrollment will not be allowed until issues are resolved. If no safety concerns are found, enrollment will continue until the target sample size is reached. The following pre-specified halting rules are provided to the DSMB as guidance.

Example of data provided to the DSMB:

- [____] of subjects with serious AE considered probably or definitely related, if >0, halting rule
- [____] of subjects with serious AE considered unrelated or only possibly related, if >50%, halting rule
- [____] of subjects with serious AE unrelated or only possibly related + [_____] number of subjects with nonserious AE of at least moderate intensity probably or definitely related, if >75%, halting rule

9.4.5 BASELINE DESCRIPTIVE STATISTICS

The DSMB will be provided with the number of subjects enrolled, stratified by sex and race/ethnicity. Mean age and range will also be provided.

9.4.6 PLANNED INTERIM ANALYSES

There will be no planned efficacy interim analyses.

9.4.7 SUB-GROUP ANALYSES

Randomization will be stratified by site (VCU and UMich) and by race/ethnicity. Two pre-specified subgroup analyses includes site and race/ethnicity.

9.4.8 TABULATION OF INDIVIDUAL PARTICIPANT DATA

Not applicable.

9.4.9 EXPLORATORY ANALYSES

Not applicable.

10 SUPPORTING DOCUMENTATION AND OPERATIONAL CONSIDERATIONS

10.1 REGULATORY, ETHICAL, AND STUDY OVERSIGHT CONSIDERATIONS

10.1.1 INFORMED CONSENT PROCESS

10.1.1.1 CONSENT/ASSENT AND OTHER INFORMATIONAL DOCUMENTS PROVIDED TO PARTICIPANTS

Informed Consent forms describing in detail the study intervention, study procedures, and risks are given to the participant and written documentation of informed consent is required prior to starting intervention/administering study intervention. The IRB-approved informed consent form is attached to this protocol as Appendix.

Potential participants will be approached by the investigators during their standard-of-care visits in the VCUHealth or UMich Sarcoidosis Clinic in private patient rooms. The investigator will review the consent form with the patients and invite them ask any questions about the study. All potential participants will be allowed to take the consent form home to review with friends/family or other health care providers. Once the potential participants have had all of their questions answered, they will be invited to sign the consent form.

Participants will not be coerced into participation. They will be advised that their refusal to participate will not affect their standard of care. All potential participants will be allowed to take the consent form home to review with friends/family or other health care providers. Participants will have as much time as needed to decide to participate or not. These are existing sarcoidosis patients that are regularly seen in the VCUHealth or UMich Sarcoidosis clinic.

10.1.1.2 CONSENT PROCEDURES AND DOCUMENTATION

Informed consent is a process that is initiated prior to the individual's agreeing to participate in the study and continues throughout the individual's study participation. Consent forms will be Institutional Review Board (IRB)-approved and the participant will be asked to read and review the document. The investigator will explain the research study to the participant and answer any questions that may arise. A verbal explanation will be provided in terms suited to the participant's comprehension of the purposes, procedures, and potential risks of the study and of their rights as research participants. Participants will have the opportunity to carefully review the written consent form and ask questions prior to signing. The participants should have the opportunity to discuss the study with their family or surrogates or think about it prior to agreeing to participate. The participant will sign the informed consent document prior to any procedures being done specifically for the study. Participants must be informed that participation is voluntary and that they may withdraw from the study at any time, without prejudice. A copy of the informed consent document will be given to the participants for their records. The informed consent process will be conducted and documented in the source document (including the date), and the form signed, before the participant undergoes any study-specific

procedures. The rights and welfare of the participants will be protected by emphasizing to them that the quality of their medical care will not be adversely affected if they decline to participate in this study.

10.1.2 STUDY DISCONTINUATION AND CLOSURE

This study may be temporarily suspended or prematurely terminated if there is sufficient reasonable cause. Written notification, documenting the reason for study suspension or termination, will be provided by the suspending or terminating party to study participants, investigators, and funding agency. If the study is prematurely terminated or suspended, the Principal Investigator (PI) will promptly inform study participants, the IRB, and sponsor and will provide the reason(s) for the termination or suspension. Study participants will be contacted, as applicable, and be informed of changes to study visit schedule.

Circumstances that may warrant termination or suspension include, but are not limited to:

- Determination of unexpected, significant, or unacceptable risk to participants
- Demonstration of efficacy that would warrant stopping
- Insufficient compliance to protocol requirements
- Data that are not sufficiently complete and/or evaluable
- Determination that the primary endpoint has been met
- Determination of futility

Study may resume once concerns about safety, protocol compliance, and data quality are addressed, and satisfy the IRB and/or DSMB.

10.1.3 CONFIDENTIALITY AND PRIVACY

Participant confidentiality and privacy is strictly held in trust by the participating investigators, their staff, and the sponsor(s) and their interventions. Therefore, the study protocol, documentation, data, and all other information generated will be held in strict confidence. No information concerning the study or the data will be released to any unauthorized third party without prior written approval of the sponsor.

All research activities will be conducted in as private a setting as possible.

The study monitor, other authorized representatives of the sponsor, representatives of the Institutional Review Board (IRB), regulatory agencies may inspect all documents and records required to be maintained by the investigator, including but not limited to, medical records (office, clinic, or hospital)

and pharmacy records for the participants in this study. The clinical study site will permit access to such records.

The study participant's contact information will be securely stored at each clinical site for internal use during the study. At the end of the study, all records will continue to be kept in a secure location for as long a period as dictated by the reviewing IRB, Institutional policies, or sponsor requirements.

Study participant research data, which is for purposes of statistical analysis and scientific reporting, will be transmitted to and stored at VCU. This will not include the participant's contact or identifying information if the subject was enrolled at UMich. Rather, individual participants and their research data will be identified by a unique study identification number. The study data entry and study management systems used by clinical sites and by VCU research staff will be secured and password protected. At the end of the study, all study databases will be de-identified and archived at VCU.

